9.2. Statistical Methods for Dose Allocation: TITE-CRM

A number of alternative designs have been proposed to the standard 3+3 design for Phase I dose escalation trials that improve its accuracy, efficiency and statistical validity, including the continual reassessment method (CRM),¹⁷ and its variants.

Delayed-onset toxicities are a particular challenge for phase I trials of combination therapies.¹⁴ Most of the available dose-escalation designs, including the 3+3 design, the up-and-down designs and the CRM design, require all patients to have completed a fixed

observation period for toxicity (eg, 1-2 cycles of the experiment regimen, or 6-8 weeks after start of treatment) before additional cohorts of patients can be enrolled. Thus, trial accrual is patient to opening and closing which may pose logistical risk on the success and completion of the study. In addition, patients who are either lost to follow-up or die of events unrelated to treatment are usually required to be replaced. Due to these reasons, the trial duration could be unacceptably long in case of prolonged observation window and unexpected high rate of patient drop-out.

The time-to-event continual reassessment method (TITE-CRM), a variant of the original CRM method, is open to accrual continually, and maintains other advantages of the CRM relative to the 3+3 design. Like CRM, TITE-CRM seeks to determine the target MTD dose, defined as the dose most closely identified with the target rate, which is the largest acceptable DLT rate determined by the investigators based on the relative costs and benefits of the treatment.

TITE-CRM is to be implemented as described by Cheung et al.³ and Normolle et al.¹⁵ for the dose-escalation of PF-05082566. PF-05082566 may be administered intravenously at the following available dose levels of 0.20, 0.45, 0.9, 1.8, 3.6, and 5 mg/kg on an every 3 week schedule (q3wk). PF-05082566 will be co-administered with MK-3475 on Day 1 of each treatment Cycle. MK-3475 will be administered at 2 mg/kg, MK-3475 will be administered q3wk. Higher dose levels may be available based on the emerging safety data from single agent PF-05082566 dosed at 5 mg/kg in the Phase 1 first-in-human study. The MTD is defined as highest dose that is associated with a DLT rate $\leq 25\%$. A power function modeling DLT rate at each dose d_i ($i=1, \dots, 6$) expressed as $\Pr(\text{DLT} \mid d_i) = F_i(\beta)$ will be used:

[figure not shown]
$$F_i(\beta) = p_i^{\exp(\beta)}$$

where p_i is the prior estimate of DLT rate at dose level d_i , and $p_1 \leq p_2 \leq \dots \leq p_6$. These estimates will be projected based model sensitivity to DLTs, together with single agent safety data for both study drugs. β is an unknown single parameter modeling the dose-toxicity relationship, with prior distribution $N(0, \sigma_0^2)$, where σ_0 is the standard deviation of the normal prior distribution with mean=0. At the beginning of the trial, the initial prior value of β is set as 0, the prior mean, which gives a prior dose-toxicity model of $F_i(\beta) = p_i$ based on the power function.

In the Bayesian paradigm, the prior distribution $N(0, \sigma_0^2)$ expresses the researchers' belief in the quality of the initial estimates p_i . The smaller the standard deviation σ_0 , the more confidence researchers have in the precision of p_i . and vice versa. As the trial progresses, this prior distribution is combined mathematically with the observed data to yield the posterior distribution of the parameter β (the posterior mean of β will be calculated to model the dose-toxicity relationship). The prior distribution determines how responsive TITE-CRM is to the accumulated data. With a small σ_0 upfront, the posterior toxicity probability estimates remain close to the prior estimates unless significantly discrepant data otherwise

occur; with a large σ_0 , the model will tend to be more immediately responsive to data. In this trial, $\sigma_0=1$, which provides a reasonably flat prior distribution of β , with 90% Bayesian credible interval of $\exp(\beta) : [0.19, 5.21]$, sufficiently wide to cover a wide spectrum of dose-toxicity scenarios. Figure 3 illustrates the dose-toxicity curve (blue curve) with 90% upper and lower bounds (red curves) when the initial prior estimates p_i are (0.01, 0.04, 0.08, 0.16, 0.25, 0.35).

Figure 3. Example Plot of Prior Dose Toxicity Curve

In the TITE-CRM paradigm, patients who have enrolled in the trial but have not experienced a DLT will be included in the probability calculation with an initial weight equal to the proportion of the 6-week (2 cycles) DLT observation period the patients have completed. However the weight function will be modified if safety data suggest different weight (toxicity) patterns in Cycle 1 and Cycle 2 of PF-05082566. An adaptive cyclical weight function as proposed by Huang et al. (2014) will be implemented.

Patients who experience a DLT or complete the observation period without a DLT will be assigned full weight (=1).

Extensive simulation results comparing the TITE-CRM using the adaptive cyclical weight function with the 3+3 design and other weight functions can be found in Huang et al. (2014)⁴⁷.

[Section 3.2](#) describes the dose escalation/de-escalation criteria, stopping rules and some restrictions and practical considerations on dose escalation.

9.3. Sample Size Determination

Due to the dynamic nature of the Bayesian allocation procedure, the sample size of the TITE-CRM approach cannot be determined in advance. The maximum sample size is set as 45 for dose escalation cohorts in order to have a reliable and accurate estimate of the MTD based on simulation results. Based on probability theory, a sample size of 45 will ensure the estimates of any binary variable (eg, objective response rate) have a 95% confidence interval of width <0.30. A sample size of 45 also enables the detection of any unexpected toxicity that occurs at 5% rate (in a non-dose-dependent fashion) with a probability of 0.90, and that occurs at 10% rate with a probability of 0.99.

A stopping rule (see [Section 3.2](#)) will also be implemented for possible early stopping if there is strong confidence in the estimated MTD.

Additional patients will be required for expansion cohorts. The total number of patients in expansion cohorts will be determined based on emerging data from this study, cancer indication, and the patient population of interest.

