## **5. GENERAL METHODOLOGY AND CONVENTIONS**

### **5.1. Hypotheses and Decision Rules**

#### **5.1.1. Hypotheses and Sample Size Determination**

No formal statistical hypothesis testing is planned.

Due to the dynamic nature of the Bayesian allocation procedure, the sample size of the Time-to-Event Continual Reassessment Method (TITE-CRM) cannot be determined in advance. The maximum sample size is set as 45 for dose escalation cohorts in order to have a reliable and accurate estimate of the MTD based on simulation results. Based on probability theory, a sample size of 45 will ensure the estimates of any binary variable (eg, objective response rate) have a 95% confidence interval of width  $<0.30$ . A sample size of 45 also enables the detection of any unexpected toxicity that occurs at 5% rate (in a non-dose-dependent fashion) with a probability of 0.90, and that occurs at 10% rate with a probability of 0.99.

A stopping rule will also be implemented if:

- Maximum sample size ( $n=45$ ) is reached; or
- 9 evaluable patients have been treated at the estimated MTD; or
- All doses appear to be overly toxic and the MTD cannot be determined in the current trial.

Additional patients will be required for expansion cohorts. The total number of patients in expansion cohorts will be determined based on emerging data from this study, cancer indication, and the patient population of interest.

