##### 6.2.2.1. Objective Response as Assessed by the Investigator per RECIST v1.1

The following analyses will be based on the FAS by treatment group. Assessment of response will be made using RECIST v1.1.

**Best Overall Response (BOR)** will be assessed based on reported overall lesion responses at different evaluation time points from the ‘start date’ until documented disease progression, according to the following rules:

- CR = at least two determinations of CR at least 4 weeks apart and before progression.
- PR = at least two determinations of PR or better at least 4 weeks apart and before progression (and not qualifying for a CR).
- SD (applicable only to patients with measurable disease at baseline) = at least one SD assessment (or better)  $\geq 6$  weeks after ‘start date’ and before progression (and not qualifying for CR or PR).
- Non-CR/non-PD (applicable only to patients with non-measurable disease at baseline) = at least one non-CR/non-PD assessment (or better)  $\geq 6$  weeks after ‘start date’ and before progression (and not qualifying for CR or PR).

- PD = progression  $\leq 12$  weeks after start date (and not qualifying for CR, PR SD, or non-CR/non-PD).
- Not Evaluable (NE): all other cases.

Only tumor assessments performed before the start of any further anti-cancer therapies will be considered in the assessment of BOR. Clinical deterioration will not be considered as documented disease progression.

**Objective Response (OR)** is defined as complete response (CR) or partial response (PR) according to RECIST v1.1 from start date until documented disease progression. Both CR and PR must be confirmed by repeat assessments performed no less than 4 weeks after the criteria for response are first met.

Patients who do not have an on-treatment radiographic tumor assessment (including due to early clinical progression), who receive anti-tumor treatments other than the study treatments prior to reaching a CR or PR, or who die, progress, or drop out for any reason prior to reaching a CR or PR will be counted as non-responders in the assessment of OR. Each patient will have an objective response status (0: no OR; 1: OR). OR rate (ORR) is the proportion of patients with OR in the analysis set.

ORR by treatment group will also be calculated along with the two-sided 95% CI using the Clopper-Pearson method (exact CI for a binomial proportion as computed by default by the FREQ procedure using the EXACT option).

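### The promised CI width below 0.30 at n=45 fails under the SAP's exact method and does not describe dose-group ORR; the detection figures hold only if the cap of 45 is reached

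*Protocol*

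**What the plan says.** Protocol 9.3 introduces the number as a ceiling: "The maximum sample size is set as 45 for dose escalation cohorts". It also says that "the sample size of the TITE-CRM approach cannot be determined in advance". It then gives three properties of 45 patients:

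- Precision: "a sample size of 45 will ensure the estimates of any binary variable (eg, objective response rate) have a 95% confidence interval of width" below 0.30. The scope is wide, since the statement covers every binary variable.
- Detection of a 5% toxicity: 45 patients "enables the detection of any unexpected toxicity that occurs at 5% rate (in a non-dose-dependent fashion) with a probability of 0.90".
- Detection of a 10% toxicity: probability 0.99.

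SAP 5.1.1 repeats all three. Neither section names the interval method behind the width.

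Protocol 3.2 and SAP 5.1.1 list the stopping rules. One ends escalation when "9 evaluable patients have been treated at the estimated MTD".

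SAP 6.2.2.1 fixes the ORR analysis: "ORR by treatment group will also be calculated along with the two-sided 95% CI using the Clopper-Pearson method". SAP 3.4.1 and 5.2 define the treatment groups as the six dose cohorts.

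**The concern.** The precision statement is a guarantee covering any binary variable, with ORR as its own example. It should therefore hold for the worst-case proportion, under the interval method the SAP will use, and for the group in which ORR will be reported. It was not evident that it met any of these conditions.

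The detection figures raise a different question. They are stated at the largest size the escalation phase can have, while another rule in the same design can end escalation sooner. No expected total, no probability of reaching 45 and no figure at a smaller total is given.

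Protocol 9.3 is the only quantitative justification of sample size in the protocol. An ethics committee could read it as promising a response interval under 30 points wide and a 90% chance of seeing a 5% toxicity. No test or decision rule depends on these figures, so what is at stake is whether the justification is accurate.

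**Working it through.** **Inputs.** Cap of 45, width below 0.30, and detection 0.90 and 0.99 (Protocol 9.3, SAP 5.1.1). Two-sided 95% Clopper-Pearson interval by treatment group (SAP 6.2.2.1). Stop at 9 evaluable patients at the estimated MTD, and at least three patients per level before escalating (Protocol 3.2). Five levels from the starting dose: 0.45, 0.9, 1.8, 3.6 and 5 mg/kg (Protocol Table 1).

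**1. The plan's figures at n=45.**

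- Wald width at p=0.5: 2 × 1.96 × √(0.25/45) = 0.292, below 0.30.
- At least one event at a 5% rate: 1 − 0.95^45 = 0.9006.
- At least one event at a 10% rate: 1 − 0.90^45 = 0.9913.

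All three reproduce. Other approximate intervals also stay below 0.30 in the worst case: Wilson 0.280, Agresti-Coull 0.280, Jeffreys 0.284.

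**2. The SAP's interval at n=45.** For x responders of n, the Clopper-Pearson limits are the 2.5% quantile of Beta(x, n−x+1) and the 97.5% quantile of Beta(x+1, n−x).

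| Responders of 45 | Exact 95% CI | Width |
|---|---|---|
| 9 | 0.096 to 0.346 | 0.250 |
| 18 | 0.257 to 0.557 | 0.2997 |
| 19 | 0.277 to 0.578 | 0.302 |
| 22 | 0.337 to 0.642 | 0.305 |
| 26 | 0.421 to 0.723 | 0.302 |

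The width is 0.30 or more for 19 to 26 responders, with a maximum of 0.305 at 22 or 23. The maximum is 0.302 at n=46 and 0.299 at n=47, so 47 is the smallest size with a guaranteed exact width below 0.30.

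**3. A dose group of 9.** The exact width is 0.336 at 0/9 or 9/9 and 0.651 at 4/9 or 5/9. No outcome gives less than 0.30.

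**4. Totals below the cap.** With no DLTs and three patients at each of the first four levels, the 9-patient rule can be met at 5 mg/kg after 3 + 3 + 3 + 3 + 9 = 21 patients.

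| Total n | Detect 5% event | Detect 10% event | Maximum exact width |
|---|---|---|---|
| 21 | 0.66 | 0.89 | 0.445 |
| 30 | 0.79 | 0.96 | 0.374 |
| 45 | 0.90 | 0.99 | 0.305 |

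**5. How often escalation ends early.** The documents give no accrual rate, so this is a range under assumptions. The TITE-CRM was simulated with the example skeleton of Protocol Figure 3, prior SD 1, linear 6-week weights and the Protocol 3.2 restrictions. There were nine toxicity scenarios with 300 runs each.

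| Assumed accrual | Median n, by scenario | Runs reaching 45 |
|---|---|---|
| One per 3 weeks | 8 to 27 | at most 1% |
| One per 1.5 weeks | 17 to 33 | at most 1.3%; 13–14% if all doses are toxic |
| One per 0.75 weeks, pausing at 9 on the current MTD | 19 to 37 (45 if all toxic) | at most 5%; about 69% if all toxic |
| One per 0.75 weeks, no pause | 25 to 45 | 16% (skeleton true), 31% (steep), 52–57% (almost no DLTs), 74% (all toxic); 1–7% otherwise |

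**The case against.** **The figures are not miscalculated.** All three reproduce at 45, and both documents tie them to that size. They also call 45 a maximum, say the size cannot be fixed beforehand, and mention possible early stopping. This stands: the detection figures are correct conditional values, not errors.

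**The exact-interval excess is tiny.** It is about 0.005, occurs only between 42% and 58% response, and disappears at 18 responders or fewer. Efficacy is descriptive only (Protocol 9.4) and no hypothesis is tested (SAP 5.1.1). This stands as to size. It does not rescue a guarantee for any binary variable when the SAP's own method breaks it.

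**A reader might infer that ORR is never computed on all patients.** That goes too far. SAP 6.2.2.1 defines ORR as a proportion of the analysis set and then adds the by-group calculation. The same section opens by placing its analyses by treatment group, so whether a pooled ORR is planned is ambiguous.

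**A reader might infer that the reported MTD group will have 9 patients.** It need not. Treatment groups are defined by dose alone, so expansion patients at the same dose would join that group. Their number is not fixed. They would also add to total safety exposure.

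**A reader might infer that escalation usually ends well before 45.** The documents do not support that without an accrual rate. Protocol 9.2 describes accrual as continuous and Protocol 3.2 discourages intentional delay; in fast unpaused runs 45 is often reached in some scenarios. The skeleton is labelled an example, the adaptive cyclical weights are not given numerically, the sponsor may overrule escalation, and doses above 5 mg/kg may be added. The simulations cited to support 45 are not shown.

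**Conclusion.** The concern holds in limited form.

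- **Precision.** The guarantee is not met under the SAP's Clopper-Pearson method, marginally at 45 (0.305 against 0.30). For ORR by dose group the shortfall is large: 0.34 to 0.65 at 9 patients, less if expansion patients enlarge the group. The result at 45 needs only the SAP's choice of interval.
- **Detection.** 0.90 and 0.99 are right at 45 and should be read as best-case values for the escalation phase. At a total of 21, which the rules permit with no DLTs, minimum cohorts and 5 mg/kg as the top level, they are 0.66 and 0.89.

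It would be wrong to conclude that the detection figures are false or that early stopping is the normal outcome. Its frequency rests on accrual, weights and a final prior that the documents do not give. This is a should-fix matter of wording.

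**What to change.** In Protocol 9.3 and SAP 5.1.1:

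1. Replace the width statement with: at most 0.31 (Clopper-Pearson) if all 45 patients are enrolled and pooled; up to 0.65 for a dose group of 9.
2. Attach the condition that all 45 patients are enrolled to the two detection figures.
3. Add detection of 5% and 10% events at smaller totals: 0.66 and 0.89 at 21; 0.79 and 0.96 at 30; 0.90 and 0.99 at 45.
4. If an expected total is given, present it as a range by assumed accrual rate, with the prior and weights stated.

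In SAP 6.2.2.1, state whether ORR is also reported over all patients.

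The cost is text only, and the stated figures become somewhat less favourable. The cap, the stopping rules, the dose levels and the specified by-group ORR analysis stay as they are.

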9.4. Efficacy Analysis

Assessment of anti-tumor activity is a secondary objective. Only descriptive efficacy summaries will be performed for this part of the study.

Tumor response will be presented in the form of patient data listings that include, but are not limited to, tumor type, received (maximum) dose, overall tumor response at each visit, and best overall response. In addition, disease progression date, death date, date of first response, and last tumor assessment date will be listed, together with Duration of Response, and PFS for the expansion cohort. Kaplan-Meier plot will be created for TTR, DR and PFS in the expansion cohort. A bar plot for TTR and DR will also be created for confirmed responders defined by RECIST 1.1.

9.5. Analysis of Other Endpoints

9.5.1. Analysis of Pharmacokinetics

9.5.1.1. Pharmacokinetics Analysis of PF-05082566 and MK-3475

Standard plasma pharmacokinetic parameters including the maximum plasma concentration (C_{max}), time to maximum plasma concentration (T_{max}), and area under the plasma concentration versus time curve (AUC) for PF-05082566 will be estimated using

non-compartmental analysis, as data permits. If data permit or if considered appropriate, minimum plasma concentration (C_{min}), average plasma concentration (C_{ave}), area under the plasma concentration versus time curve to infinity (AUC_{inf}), terminal elimination half-life ($t^{1/2}$), total systemic clearance (CL), volume of distribution (Vd), accumulation ratio (Rac) will be estimated. Descriptive statistics will be provided for these PK parameters in tabular form (n, mean, SD, CV, median, minimum, maximum, geometric mean and its associated CV) by dose, cycle and day.

Dose normalized AUC_{inf} (AUC_{τ} at steady state), AUC_{last} , and C_{max} for PF-05082566 may be plotted against dose (using a logarithmic scale). These plots will include individual patient values and the geometric means for each dose. These plots will be used to help understand the dose proportionality for PF-05082566.

For MK-3475, plasma pharmacokinetic parameters will be determined by Merck using a validated population pharmacokinetic model.

For PF-05082566 and MK-3475 concentrations, individual values and descriptive statistics (n, mean, SD, CV, median, minimum, maximum, geometric mean and its associated CV) will be presented by dose, cycle, day of assessment, and nominal time in tabular form. Individual patient and median profiles of the concentration-time data will be plotted by dose, cycle and day using nominal times. Median profiles will be presented on both linear-linear and log-linear scales.

No drug interaction is anticipated between PF-05082566 and MK-3475. Since PF-05082566 and MK-3475 are eliminated via a non-specific catabolic degradation process, it is unlikely that concomitant medication can alter their clearance even if target expression is affected. To assess any potential interactions, steady state pharmacokinetics and the formation of anti-drug antibodies will be monitored for both the agents and compared with historical data.

9.5.1.2. Population Pharmacokinetic Analysis or PK CCI Modeling

Pharmacokinetic CCI data from this study may be analyzed using modeling approaches and may also be pooled with data from other studies to investigate any causal relationship between PF-05082566/ MK-3475 exposure and biomarkers or significant safety endpoints. The results of these analyses, if performed, may be reported separately.

9.5.1.3. Analysis of Immunogenicity Data

ADA data will be listed and summarized for each dosing interval for PF-05082566 and MK-3475. The effect of ADA on PF-05082566 and MK-3475 concentration will be evaluated.

9.5.1.4. Statistical Analysis of Biomarker Endpoints

For tumor biopsy samples, the mean and standard deviation, median, and minimum/maximum levels of biomarker measures, including but not limited to percentage of CD3-positive T cells, will be determined at baseline and post-treatment. For each pair of

specimens, the percent change from baseline of these same parameters will also be calculated. The minimum percent change from baseline needed to declare proof of pharmacology will be based on assay precision and size of the expansion cohort.

CCI [REDACTED] The statistical approach will examine correlations of biomarker results with pharmacokinetic parameters and measures of anti-tumor efficacy.

CCI [REDACTED]

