While preclinical data demonstrated significant immunomodulatory activity and anti-tumor activity of PF-05082566 when dosed as a single agent, it is hypothesized that in some tumors upregulation of PD-1 on tumor-infiltrating lymphocytes, and its ligand PD-L1 on tumor cells, may down-modulate the activity of anti-tumor lymphocytes stimulated by an agonist anti-4-1BB antibody. PD-L1 may be expressed on tumor cells as a result of activated T cells within the tumor producing inflammatory cytokines, such as interferon gamma (IFN- γ). In accord with this, studies in mice suggest that activated tumor-infiltrating T lymphocytes (TILs) induce the expression of PD-L1, which in turn results in down modulation of the Tcells. This is thought to be one mechanism for tumor cell evasion of the immune system. Tumor cells expressing PD-L1 may be better candidates for anti-PD-1 therapies than tumors that do not express PD-L1. It is clear from the study of biopsies that many tumors do not contain detectable numbers of infiltrating T cells, which could account in part for lack of PD-L1 expression in many of these tumors. In theory, an agonist anti-4-1BB antibody may activate T cells, which can traffic to tumors that would not otherwise contain these activated cells, where they may induce the expression of PD-L1. Therefore, the local environment

within tumors that do not respond to anti-PD-1 therapies or anti-4-1BB single agent therapies may be converted to an immune responsive environment by combining an anti-PD-1 antagonist antibody with an anti-4-1BB agonist antibody. In support of this concept, an agonist anti-4-1BB antibody in combination with an anti-PD-1 antagonist antibody showed significantly improved anti-tumor activity compared with either single agent in multiple mouse models. In addition, safety data in mice indicated that the addition of an anti-PD-1 antibody did not add to the toxicity of an anti-4-1BB agonist antibody.

STUDY OBJECTIVES AND ENDPOINTS

Objectives

Primary Objectives

- To estimate the Maximum Tolerated Dose (MTD) and select the Recommended Phase 2 Dose (RP2D) for the combination of PF-05082566 with MK-3475 in patients with advanced solid cancer.

Secondary Objectives

- To evaluate the overall safety profile;
- To characterize the pharmacokinetics of PF-05082566 and MK-3475 given in combination following IV administration;
- To evaluate the immunogenicity of PF-05082566 and MK-3475 when given in combination;

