7.6. Tumor Biopsies for Mechanistic Exploratory Biomarkers

Tumor growth inhibition following treatment with 4-1BB agonist monoclonal antibodies or with PD-1 antagonist monoclonal antibodies has been associated with increases in tumor-infiltrating lymphocytes. Paired de novo tumor biopsies are mandatory for the patients enrolled in the expansion cohorts in order to determine whether the combination of PF-05082566 and MK-3475 has this effect. A de novo biopsy will be required at study entry followed by a second biopsy at the time of the Cycle 3 tumor assessment. For patients in dose escalation cohorts, unscheduled optional de novo tumor biopsies may be collected at the discretion of the Sponsor and Investigator to support the assessment of disease progression. Biomarkers that will be assayed may include but will not be limited to IHC assessment of tumor-infiltrating lymphocytes, PD-L1 IHC, quantitation of T cell receptor sequences, and gene expression.

Please refer to the Study Manual for details pertaining to specific days of sample collection, and sample preparation and shipping

CCI

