#### 6.2.5. Biomarker Endpoints

For tumor biopsy samples, the mean and standard deviation, median, and minimum/maximum levels of biomarker measures, including but not limited to percentage of CD3-positive T cells, will be determined at baseline and post-treatment. For each pair of specimens, the percent change from baseline of these same parameters will also be calculated. The minimum percent change from baseline needed to declare proof of pharmacology will be based on assay precision and size of the expansion cohort.

CCI The statistical approach will examine correlations of biomarker results with pharmacokinetic parameters and measures of anti-tumor efficacy.

CCI

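### The proof-of-pharmacology criterion for the paired biopsies rests on percent change from baseline, which has no value at a zero T-cell baseline and is unstable near zero

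*Protocol*

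**What the plan says.** Protocol 7.6 explains why the tissue is taken: "Paired de novo tumor biopsies are mandatory for the patients enrolled in the expansion cohorts", in order to learn whether the combination raises tumour-infiltrating lymphocytes. Protocol 9.5.1.4 and SAP 6.2.5 give the analysis in matching words. Levels of the biomarkers are summarised before and after treatment (mean, SD, median, minimum and maximum). The one measure named is the "percentage of CD3-positive T cells, will be determined at baseline and post-treatment". Then, for each biopsy pair, "the percent change from baseline of these same parameters will also be calculated". The decision sentence follows: "The minimum percent change from baseline needed to declare proof of pharmacology will be based on assay precision and size of the expansion cohort". No numerical threshold is given.

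The Study Rationale in the Protocol Summary describes the tumours of interest: "It is clear from the study of biopsies that many tumors do not contain detectable numbers of infiltrating T cells". It proposes, as theory, that a 4-1BB agonist may activate T cells "which can traffic to tumors that would not otherwise contain these activated cells". It adds that tumours which do not respond to either class of agent alone may become immune-responsive under the combination.

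**The concern.** The criterion uses a ratio whose denominator is the baseline T-cell measure, and the rationale expects that measure to be undetectable in many tumours. Where it is zero, the change statistic does not exist. Where it is just above zero, the statistic is dominated by counting noise. The pairs closest to the hypothesis, empty at entry and infiltrated at week 9, are therefore the ones that the stated statistic cannot score.

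What is at stake is how far a declaration of proof of pharmacology can be trusted. Mechanism in tumour tissue is a secondary objective for the expansion cohorts, and the patients must undergo both biopsies.

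**Working it through.** The plan gives no sample size, power or threshold for this analysis, so there is no figure to reproduce. The check concerns the statistic itself.

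**Inputs from the documents**
- Change statistic and criterion: percent change (Protocol 9.5.1.4, SAP 6.2.5).
- Share of tumours without T cells: described as many, with no rate (Protocol Summary).
- Number of pairs: not fixed (Protocol 9.3).
- Biomarker analysis set: a baseline and at least one on-study value, with no requirement of a non-zero baseline (SAP 4.3.3).
- Missing data: as observed, without imputation unless otherwise specified (SAP 5.3.1).
- Values below quantification: a rule for PK concentrations only (SAP 5.3.1.1).

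**Step 1. One rise on two scales.** Percent change = 100 × (post − pre)/pre. With a rise of 5 percentage points this is 100 × 5/pre:

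| Baseline CD3+ | Percent change | Absolute change |
|---|---|---|
| 0% | undefined | +5 |
| 0.1% | +5000% | +5 |
| 0.5% | +1000% | +5 |
| 1% | +500% | +5 |
| 5% | +100% | +5 |
| 10% | +50% | +5 |
| 20% | +25% | +5 |

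The ordering can also reverse. A move from 0.1% to 0.5% is 100 × 0.4/0.1 = +400% for 0.4 points. A move from 20% to 30% is 100 × 10/20 = +50% for 10 points.

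**Step 2. Noise with no true change.** Assume 1000 cells counted per specimen and independent binomial counts with the same true share p before and after treatment. The chance of a zero baseline count is (1 − p)^1000. The chance of an apparent rise of at least 100% is P(post ≥ 2 × pre), given pre > 0:

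| True CD3+ share | Zero baseline count | Apparent rise ≥100%, given non-zero baseline |
|---|---|---|
| 0.1% | 37% | 16% |
| 0.2% | 14% | 23% |
| 0.5% | 0.7% | 18% |
| 1% | about 0 | 8% |
| 5% | about 0 | 0.04% |

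The 1000 cells and the 100% cut are assumptions; the documents give neither.

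**Step 3. A cohort average.** Assume 20 pairs, a true rise of 5 points in every pair, and baselines that are lognormal with median 2% and log-SD 1.5. Over 5000 simulated cohorts, the typical mean percent change was about +650% and the typical median about +250%. The largest single pair typically supplied about 30% of the total. On the absolute scale every pair contributes +5.

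**Step 4. Pairs without a value.** Pairs lost to percent change = N × f, where f is the share with a zero baseline. For N = 20 and f from 20% to 50%, this is 20 × 0.20 = 4 to 20 × 0.50 = 10. Both N and f are assumptions, so this shows sensitivity and is not an estimate for this trial.

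**The case against.** The strongest reply is that little depends on this statistic.

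- **Levels are kept.** Levels at both times come first and percent change is additional. A reader might infer that converted tumours drop out of the mechanism objective. The documents do not support that: a 0% to 10% pair stays in the biomarker analysis set and in both level summaries, and SAP 5.3.1 has statistics that cannot be calculated displayed as such. The objective also draws on T-cell receptor sequences, gene expression and PD-L1 staining (Protocol 7.6). This part of the reply stands.
- **No per-pair verdict is stated.** A reader might infer that each pair passes or fails a threshold such as +100%, and that the eventual conclusion must be wrong. The documents say neither how pairs are judged nor how they are combined, and a threshold that depends on cohort size may well apply to the cohort. This stands. However, a cohort mean of percent changes has the weakness shown in Step 3. A median resists extremes but still has no value for zero-baseline pairs.
- **Assay precision informs the threshold.** This may allow for some low-baseline noise. It cannot give a value to a zero baseline. A percent threshold high enough to exclude that noise would also exclude large absolute rises in well-infiltrated tumours.
- **Redaction.** Blacked-out text follows the criterion in both documents and could contain a handling rule. This stands as a limit on the finding.
- **Frequency.** The remark about many tumours is general background, the expansion tumour types are not settled, and tumours lacking activated T cells need not have zero CD3. No count of affected pairs can be drawn from the documents.

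**Conclusion.** The point holds in limited form. As written, the criterion rests on a statistic that cannot be computed at a zero baseline and is unstable near zero. The protocol's own rationale makes such baselines likely and central to the hypothesis. The readable text has no rule for them; the redacted text might.

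The defect is confined to the change statistic and the declaration built on it. The underlying levels are summarised, so other scales could be calculated later, although a scale chosen after seeing the results would make a weaker basis for a declaration. The size in this trial is unknown because the zero-baseline share, the number of pairs, the assay limit and the threshold are all unstated. The arithmetic in Step 1 needs no assumption; Steps 2 to 4 are illustrations. The endpoint is secondary, limited to the expansion cohorts and without formal testing. The MTD and DLT analysis is unaffected.

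**What to change.** In Protocol 9.5.1.4 and SAP 6.2.5:

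1. Base the proof-of-pharmacology criterion on a change measure that is defined at zero. This can be absolute change, or log2[(post + c)/(pre + c)] with c fixed at the assay's quantification limit.
2. Set the threshold on that scale from assay precision, and record it before the post-treatment readouts are analysed.
3. Tabulate conversion from undetectable at baseline to detectable at week 9 as its own category.
4. Report percent change descriptively only, for pairs with a baseline above the quantification limit.

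If the redacted text already contains a zero-baseline rule, the sponsor should confirm that it also governs the criterion.

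The cost is a small rewording of both documents and a scale that readers may find less familiar. With the log ratio, results at low baselines depend on c, so c must be fixed in advance. No new specimens or assays are needed.
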